11.1.3. EQ-5D-5L

Five dimensions of the EQ-5D-5L include 'mobility', 'selfcare', 'activity', 'pain', and 'anxiety'. The US Pickard value set will be used to compute the EQ-5D-5L index values. The value set will be denoted as disut_mo for 'mobility', disut_sc for 'selfcare', disut_ua for 'activity', disut_pd for 'pain', and disut_ad for 'anxiety' in [Table 7](#) below:

Table 7: EQ-5D-5L Value Set

		US value set
MOBILITY		disut_mo
I have no problems in walking about	1	0
I have slight problems in walking about	2	0.096
I have moderate problems in walking about	3	0.122
I have severe problems in walking about	4	0.237
I am unable to walk about	5	0.322
SELF-CARE		disut_sc
I have no problems washing or dressing myself	1	0
I have slight problems washing or dressing myself	2	0.089
I have moderate problems washing or dressing myself	3	0.107
I have severe problems washing or dressing myself	4	0.220
I am unable to wash or dress myself	5	0.261
USUAL ACTIVITIES		disut_ua
I have no problems doing my usual activities	1	0
I have slight problems doing my usual activities	2	0.068
I have moderate problems doing my usual activities	3	0.101
I have severe problems doing my usual activities	4	0.255
I am unable to do my usual activities	5	0.255
PAIN / DISCOMFORT		disut_pd
I have no pain or discomfort	1	0
I have slight pain or discomfort	2	0.060
I have moderate pain or discomfort	3	0.098
I have severe pain or discomfort	4	0.318
I have extreme pain or discomfort	5	0.414
ANXIETY / DEPRESSION		disut_ad
I am not anxious or depressed	1	0
I am slightly anxious or depressed	2	0.057
I am moderately anxious or depressed	3	0.123
I am severely anxious or depressed	4	0.299
I am extremely anxious or depressed	5	0.321
We would like to know how good or bad your health is TODAY	0 to 100	

$disut_total = disut_mo + disut_sc + disut_ua + disut_pd + disut_ad$;

The EQ-5D-5L index value (EQindex) = $1 - disut_total$

The SAS code will be provided in Appendix [Section 11.5](#)

11.2. Table of Contents for Data Display Specifications

Table of contents for data display specifications will be provided in a separate document.

11.3. Data Display Specifications

Data display specifications will be provided in a separate document.

11.4. Analysis Windows

Measurements collected during the 24-week double-blind placebo-controlled period will be included only in the analysis windows up to Week 24. For data collected at a scheduled post randomization, the analysis visit will be the nominal visit as collected and visit window will not be applied.

For unscheduled or early discontinuation post randomization, analysis visit will be used according to [Table 8](#) below when the scheduled visit is not available.

Table 8: Analysis Windows for Measurements

Visit	Scheduled Day	Lower Bound	Upper Bound
Screening	<1	<1	<1
Day 1	1	1	1
Week 2	15	2	21
Week 4	29	22	35
Week 6	43	36	49
Week 8	57	50	70
Week 12	85	71	98
Week 16	113	99	126
Week 20	141	127	154
Week 24	169	155	196
Week 28/Follow-up	last dose + 28 days	-	-

Note: Week 28/Follow-up should occur 4 weeks after last dose. The analysis visit of week 28/Follow-up will include the nominal visit End of Study (Week 28) and any unscheduled visits occurred after the week 24 window.

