CGI = Clinical Global Impression scale; CMR = cardiac magnetic resonance imaging; CPET = cardiopulmonary exercise testing; ECG = electrocardiogram; Echo = echocardiogram; ED = early discontinuation; EOS = end of study; EOT = end of treatment; EQ-5D-5L = EuroQol 5-dimension 5-level instrument; hs-cTnI = high sensitivity cardiac troponin I; IP = investigational product; IWRS = interactive web response system; KCCQ = Kansas City Cardiomyopathy Questionnaire; NT-proBNP = n-terminal prohormone brain natriuretic peptide; NYHA = New York Heart Association; SAQ-7 = Seattle Angina Questionnaire-7; PGI-C = Patient Global Impression of Change scale; PK = pharmacokinetic; WOCBP = women of childbearing potential; PT-INR = prothrombin time/international normalized ratio; UNS DILI = unscheduled drug-induced liver injury

^a The CPET must be completed within four weeks but not less than one week prior to randomization.

- ^b If a patient is temporarily unable to exercise on the treadmill or bicycle (whichever modality was used at baseline) due to an adverse event (eg, ankle sprain, upper respiratory infection, migraine), but not due to HCM symptoms, or if the site is unable to perform CPET (eg, equipment malfunction), then the Week 24 visit may be postponed by up to 4 weeks. The patient should continue to receive IP until the visit. Sites should contact patients shortly before the Week 24 visit and confirm their ability to perform CPET. If necessary, the Week 24 visit may be split across two consecutive days within the visit window. If the visit is split, all assessments, except the CPET, should occur on the first day of the split visit. The CPET should occur on the second day of the split visit. Dosing will occur on site on both split visit days.
- ^c The EOS visit (Week 28) will occur 4 weeks after last dose. It is not required for patients who discontinue IP >4 weeks prior to the Week 24.
- ^d Patients who withdraw from the trial IP should complete an early discontinuation visit as soon as possible if they no longer wish to be part of the study. An EOS visit should be performed 4 weeks after their final IP dose if possible.
- ^e Height is measured at the Screening visit only.
- ^f Vital signs include heart rate, respiratory rate, and blood pressure. Oxygen Saturation only done at Screening.

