7.2.1. Management of Patients after Permanent Discontinuation of IP

If IP is permanently discontinued, the patient should be encouraged to remain in the trial to continue to obtain outcome measures and safety data (see Section 7.2).

There are several options for a patient after permanently discontinuing IP:

- Patient agrees to continue to return to clinic for all remaining trial visits.
- Patient agrees to complete the early discontinuation (ED) visit as soon as possible after the decision is made and complete an EOS visit.
- Patient only agrees to complete the ED visit.
- Patient agrees to be contacted by phone to obtain patient trial data.
- Patient withdraws consent (see Section 7.4) and does not agree to any further trial procedures or visits.
- For those patients who have not withdrawn consent and have difficulty returning for all remaining trial visits, they can be contacted by phone to obtain patient trial data.

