5.7.6. Analysis Windows

Since study visits do not always take place exactly as scheduled per protocol, it is necessary to assign the actual observation dates to analysis windows for analysis purposes.

For data collected at a scheduled post baseline visit, the analysis visit will be assigned based on the scheduled nominal visit as collected on the eCRF.

For unscheduled or early discontinuation post baseline visits, measurements taken on or after the first dose of study drug will be assigned to an analysis window using defined lower and upper bounds for each analysis window. Measurements assigned in an analysis window will have study day greater than or equal to the lower bound but no greater than the upper bound of the analysis window. The lower bound and the upper bound for the analysis windows are defined as the midpoints between the scheduled visits for all assessments (see [Section 11.4](#)).

Visits are identified as the nominal visits according to the eCRFs. Each visit will be identified with the visit descriptor (eg, “Week 24”).

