For the proportion of patients with ≥ 1 class improvement in NYHA class at Week 12, Week 16 NYHA class will be used if Week 12 NYHA class is not available. Week 8 NYHA class will be used if Week 16 NYHA is not available. Patient will be considered as not achieving ≥ 1 improvement in NYHA class at Week 12 if no NYHA at Weeks 8, 12 and 16 is available. Similarly, Week 20 NYHA class will be used if Week 24 NYHA is not available. Patient will be considered as not achieving ≥ 1 improvement in NYHA class at Week 24 if Week 20 and Week 24 NYHA are not available. A sensitivity analysis will be performed by repeating Cochran–Mantel–Haenszel (CMH) test by assigning missing NYHA class at Weeks 12 and 24 as non-responders. Proportion of patients with ≥ 1 class improvement in NYHA class will be analyzed using CMH test stratified by randomization factors. The p-value and 95% CI will be obtained using exact method.

Subgroup analysis will be done by repeating the CMH test for each subgroup level without specifying stratifying by randomization stratification factors.

4. Proportion of patients with post-Valsalva LVOT-G < 30 mmHg at Weeks 12 and 24

For the proportion of patients with post-Valsalva LVOT < 30 mmHg at Week 12, Week 16 post-Valsalva LVOT will be used if Week 12 visit is performed but post Valsalva LVOT is not available. Week 8 post-Valsalva LVOT will be used if Week 16 is not available. Similarly, Week 20 post Valsalva LVOT will be used if Week 24 is performed but post Valsalva LVOT is not available.

Proportion of patients with post-Valsalva LVOT-G < 30 mmHg at Weeks 12 and 24 will be analyzed using Cochran–Mantel–Haenszel (CMH) test stratified by randomization factors. The p-value and 95% CI will be obtained using exact method.

Subgroup analysis will be done by repeating the CMH test for each subgroup level without specifying stratifying by randomization stratification factors.

- Total duration of SRT eligibility during the 24-Week treatment period in patients who were SRT eligible at baseline

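### SAP Table 8 files every End of Study visit under Week 28/Follow-up whatever its study day, so some leavers' off-drug Week 24 (less often Week 12) values go unused and, for NYHA class, an earlier value is carried in

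*SAP*

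**What the plan says.** SAP 11.4 deals with visits by type.

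- Scheduled visits: "the analysis visit will be the nominal visit as collected and visit window will not be applied".
- ED and unscheduled visits are placed by study day (SAP 5.7.6: "For unscheduled or early discontinuation post baseline visits, measurements taken on or after the first dose of study drug will be assigned to an analysis" …). The bounds are "defined as the midpoints between the scheduled visits for all assessments".
- EOS: Table 8 gives the scheduled day as last dose + 28 days, prints no lower or upper bound, and adds the note "The analysis visit of week 28/Follow-up will include the nominal visit End of Study (Week 28".

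The protocol lets EOS fall early. Among the options after stopping drug, Protocol 7.2.1 lists agreeing to "complete the early discontinuation (ED) visit as soon as possible after the decision is made and complete an EOS visit". Footnote d of the Schedule of Activities says of patients who withdraw: "An EOS visit should be performed 4 weeks after their final IP dose if possible". The EOS visit includes NYHA class, KCCQ and a full echocardiogram, but no CPET.

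For NYHA responders, SAP 7.8.1 says "Week 20 NYHA class will be used if Week 24 NYHA is not available", without requiring that a Week 24 visit took place. For Week 12 the fallback is Week 16, then Week 8.

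Two other SAP sentences point the other way. SAP 11.4 opens with "Measurements collected during the 24-week double-blind placebo-controlled period will be included only in the analysis windows up to Week 24", and SAP 7.8.1 puts everything observed up to Week 24 into the MMRM.

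**The concern.** Protocol 4.1 follows patients whether or not they remain on drug, and the full analysis set is all randomized patients. Under that aim, a value observed off drug on the Week 24 target day is the value wanted at Week 24. The Table 8 note moves it to follow-up because of its visit name. The NYHA rule then treats Week 24 as unavailable and takes an earlier class, usually recorded on drug.

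Protocol 2.3.1 describes the drug's effect as readily reversible on stopping. An on-drug class is therefore a poor stand-in for one taken four weeks after the last dose. Placebo patients have no drug effect to lose, so the substitution tends to favour an effective active arm. NYHA is Step 3 (Week 24) and Step 8 (Week 12) of a fixed sequence, so it is a formally tested endpoint that also gates later steps.

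Because the note conflicts with the two sentences cited above, two programmers could also map the same record differently.

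**Working it through.** **1. Table 8 bounds.** The printed upper bounds follow the midpoint with the next scheduled day, minus 1:

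- Week 8: (57 + 85)/2 − 1 = 70, as printed.
- Week 12: (85 + 113)/2 − 1 = 98, as printed.
- Week 20: (141 + 169)/2 − 1 = 154, as printed.
- Week 24: (169 + 197)/2 − 1 = 182, but the table prints 196. Day 197 is not printed; it is last dose + 28 for a last dose on Day 169.

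**2. Where EOS falls** (EOS day = last-dose day + 28).

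- Week 24 window, Days 155–196: last doses on Days 127 (155 − 28) to 168 (196 − 28).
- Week 12 window, Days 71–98: last doses on Days 43 (71 − 28) to 70 (98 − 28).
- An on-time completer with last dose on Day 169 has EOS on Day 197, outside the window, so the note does no harm there.
- At last dose + 35, the end of the +7-day visit window, the Week 24 range moves to last doses on Days 120–161.

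**3. One patient traced.** Last dose Day 141, ED Day 145, EOS Day 169. The ED record falls in the Week 20 window (127–154) and yields to the scheduled Week 20 visit under SAP 5.7.7. The EOS record is on the Week 24 target day but is labelled follow-up. Week 24 NYHA is then unavailable and the Day 141 on-drug class is used.

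**4. Which last doses are exposed at Week 24** (visits on their scheduled days).

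- Days 155–168: the ED visit comes after the last dose, so it supplies Week 24 unless held after Day 196. Generally unaffected.
- Days 127–154 (28 days): the EOS value is lost to Week 24, unless the ED visit is on Day 155 or later.
- Within these, Days 141–154 (14 days): a scheduled on-drug Week 20 class exists and is carried in.
- Days 127–140: no scheduled Week 20 visit. An ED record in Days 127–154 becomes Week 20, so the carried class is from soon after stopping. With no such record the patient is a non-responder.

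**5. Size at Week 24.** Assumptions not in the documents: 3–10% of 135 per arm stop early, uniformly over 168 days, and all choose ED plus EOS. One patient is 1/135 = 0.74 points.

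| | 3% (4.05 stoppers) | 10% (13.5 stoppers) |
|---|---|---|
| EOS value lost (× 28/168) | 0.68 | 2.25 |
| Scheduled Week 20 class carried in (× 14/168) | 0.34 | 1.13 |
| Most it can move NYHA, scheduled Week 20 only | 0.25 points | 0.83 points |
| Most it can move NYHA, ED-as-Week-20 also counted | 0.5 points | 1.67 points |

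The maxima need every affected patient to be a responder on the carried value and a non-responder at EOS. If Week 20 is held at Day 134, the edge of its window, Days 134–154 count: 13.5 × 21/168 = 1.7 patients at 10%.

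**6. Week 12.** The same arithmetic applies (28 and 14 of 168 days; a scheduled Week 8 value needs a last dose on Days 57–70). These cases should be rarer, because footnote c says EOS is not required when drug stops more than four weeks before Week 24. With a last dose on Days 43–49, an ED visit in the Week 6 window and no Week 8 record, the patient becomes a non-responder.

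**7. Effect by endpoint.**

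- NYHA (Steps 3, 8): earlier class carried in.
- KCCQ-CSS and LVOT-G change (Steps 2, 4, 7, 9): missing in the MMRM; nothing substituted.
- LVOT-G below 30 mmHg (Steps 5, 10): the fallback requires that the Week 12 or 24 visit was performed, so none is stated for a leaver.
- SRT duration (Step 6): the carried class can enter through adjacent-visit imputation, but only for visits before Week 24. The SAP's worked cases 4 and 5 differ only at Week 24 and both give 14 weeks.
- pVO2 and total workload: no CPET at EOS or ED, so nothing to lose.

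**The case against.** The strongest reply is that the SAP already says otherwise: the opening sentence of 11.4 and the MMRM wording in 7.8.1 can both be read to bring in a Day 85 or Day 169 record. That shows the text is inconsistent, but it does not settle the mapping. A leaver's EOS is post-dose follow-up, and the note names that visit explicitly.

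Several limits do stand. A reader might infer that all early stoppers lose their off-drug data. They do not: Protocol 7.2.1 encourages stoppers to stay, and those who keep attending have nominal Week 12 and Week 24 visits that are used. A reader might also infer that on-drug values replace observed ones across Steps 2–4 and 7–9. The documents support replacement for NYHA only. For the MMRM endpoints the value is missing, and a sensitivity analysis imputes monotone missing data from a placebo-built model. For NYHA, a sensitivity analysis treats missing Week 12 and 24 classes as non-response. These help, but they are not the tested analyses.

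Footnote c also reduces exposure. Read literally, it covers every Week 12 case and last doses on Days 127–140. Protocol 8.1.5 limits the exemption to patients who stay for all follow-up, and asks those leaving for an EOS visit if possible. The two texts need reconciling.

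Finally, the Week 24 bound of 196 is plausibly deliberate, since the protocol lets Week 24 slip by up to four weeks. It is an unstated exception rather than a demonstrated error.

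**Conclusion.** The point holds in limited form. The Table 8 note sets aside off-drug values that fall in the Week 24 window, and less often the Week 12 window, for patients who leave by ED plus EOS. For NYHA it lets an earlier, usually on-drug, class stand in. The data are relabelled as follow-up rather than deleted.

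Under the stated assumptions about 0.7–2.3 patients per arm lose an EOS value at Week 24, and 0.3–1.1 of them have a scheduled Week 20 class carried in. That is at most about 0.8 points on an arm's NYHA proportion, or 1.7 points if ED records used as Week 20 are counted. Counting all last doses on Days 127–168 would suggest 42/168 = 25% of stoppers, but this overlooks the ED visits that already supply Week 24 for Days 155–168. Neither document gives a stop rate, its timing or the uptake of each option.

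The effect is small, but it touches tested endpoints, runs against follow-up irrespective of treatment, and is easily removed. It should be corrected; it does not threaten the primary result.

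**What to change.** - In SAP 5.7.6 and the Table 8 note, assign an EOS visit by study day, as for ED visits, when no nominal Week 24 visit precedes it and no scheduled record exists in that window. Where an ED record shares the window, the closest-day rule in SAP 5.7.7 already chooses between them.
- Keep the Week 28/Follow-up label for EOS visits that come after the Week 24 visit.
- Apply the NYHA and LVOT fallbacks, including those feeding SRT duration, only after this mapping.
- Align the note with the first sentence of SAP 11.4 and the MMRM wording in 7.8.1.
- State that the Week 24 upper bound of 196 is an exception to the midpoint rule, with its reason.
- Reconcile footnote c of the Schedule of Activities with Protocol 8.1.5 on when EOS is expected.

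The cost is SAP wording and a line of visit-mapping code before database lock, with no new data. A few off-drug values will enter the analysis, so estimates may be slightly less favourable.

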11.5. Sample SAS Codes

ANCOVA model for primary endpoint

```
proc mixed data=work;  
  class <treatment arm (ref='0')> <Beta Blocker use> <Exercise Modality>;  
  model chg=<base pvo2 > <base weight> <treatment arm> <beta blocker use> <Exercise  
  Modality> /solution s Influence(EFFECT=usubjid) outp=out vciry;  
  lsmeans <treatment arm>/pdiff cl;  
  ods output solutionf=mixparms covB=mixcovb;  
run;
```

This code assumes that the analysis involves 2 levels in treatment arm (e.g., placebo group is coded as 0 and aficamten is coded as 1).

MMRM model

```
proc mixed data=work;  
  class <Subject> <treatment arm (ref='0')> <Beta Blocker use> <Exercise Modality> <visit>;  
  model <chg> = <base> <treatment arm> <visit> <visit>*<treatment arm> <Beta Blocker use> <Exercise  
  Modality> <visit>*<base>/ddfm=kenwardroger;  
  repeated <visit> / type=un subject=<Subject>;  
  lsmeans <visit>*<treatment arm>/cl pdiff;  
run;
```

This code assumes 2 level in treatment arm with placebo group is coded as 0. visit has level of nominal visit week where continuous measurements are assessed up to Week 24.

Imputation model for primary endpoint

```
proc mi data=work seed=&seed out=miout NIMPUTE=50;  
  class <treatment arm> <Beta Blocker use> <Exercise Modality> <base NYHA> <randomization  
  factors>;  
  var <treatment arm> <randomization stratifications> <sex> <age> <base pVO2> <base  
  hemoglobin> <base KCCQ CSS> <baseline NYHA> <last available post rand NYHA> <last  
  available post rand resting LVOT> <last available post rand Valsalva LVOT> <W24 pVO2> ;  
  monotone reg(W24 pVO2);  
run;
```

Placebo-based imputation for sensitivity analysis of the primary endpoint

Step 1:

generate input dataset for subjects in placebo group or subject who didn't complete treatment, and datasets for the rest of subjects in aficamten group.

Step2: impute missing data with separately with each input dataset using the imputation model for the primary endpoint.

Step 3. Combined the complete data from the imputations above as final imputed dataset.

Tipping point imputation for primary endpoint

```
proc mi data=work seed=&seed out=miout NIMPUTE=50;  
  class <treatment arm> <Beta Blocker use> <Exercise Modality> <base NYHA> <>;  
  var <treatment arm> <sex> <age> <base pVO2> <base hemoglobin> <base KCCQ CSS>  
  <baseline NYHA> <last available post rand NYHA> <last available post rand resting LVOT>  
  <last available post rand Valsalva LVOT> <W24 pVO2> ;  
  monotone reg(W24 pVO2);  
  mmar adjust (W24 pVO2/shift=&shift adjustobs=(Trt='1'));  
run;
```

shift will be set so that the imputed value for aficamten group is 1 ml/min/kg worse as starting point with increment of 1 ml/min/kg worse each time until the result is no longer significant.

Multiple Imputation for sensitivity analysis for repeated measures endpoint

Step 1:

```
proc mi data=work1 seed=&seed1 out=miout1 NIMPUTE=100;
  by <treatment arm>;
  mcmc IMPUTE=monotone ;
  var <base> <var week 2> <var week4> <var week6> <var week8> <var week12> <var week16>
<var week20> <var week24>;
run;
```

Step 2:

```
proc mi data=miout1 seed=&seed NIMPUTE=1 OUT=miout2;
  class <treatment arm>;
  by _IMPUTATION_;
  var <treatment arm> <base> <var week 2> <var week4> <var week6> <var week8> <var week12> <var
week16> <var week20> <var week24>;
  monotone reg (<base> <var week 2> <var week4> <var week6> <var week8> <var week12> <var
week16> <var week20>);
  mmar model (<base> <var week 2> <var week4> <var week6> <var week8> <var week12> <var
week16> <var week20> / modelobs = (trt01pn = '0'));
run;
```

Multiple Imputation for categorical endpoint

```
proc mi data=work seed=&seed out=outwork NIMPUTE=100;
  class <var at week8> < var at week 12> < var at week 16> < var at week 20> < var at week 24>
<treatment arm>;
  var <treatment arm> <var at week8> < var at week 12> < var at week 16> < var at week 20> < var at
week 24> ;
  fcs logistic (<var at week8> < var at week 12> < var at week 16> < var at week 20> < var at week 24> =
<treatment arm> /link=glogit);
run;
```

SAS codes using proc mianalyze to combine results from imputed datasets

The pooled estimates from the 50 imputed datasets are obtained from the following codes.

```
proc mianalyze data=est;
  modeleffects estimate;
  stderr stderr;
run;
```

Mixed model for CPET data

```
proc mixed data=work;
  class <subject ID> <visit> <stratification factors> ;
  model <chg in CPET>=<trtid> <stratification factors> <stratification factors>*<visit> /s;
  estimate 'active at Week 24' int 1 <trtid> 1 <stratification factors> &c1 &c2 stratification
factors>*<visit> 0 0 &c1 & / e;
  estimate 'placebo at Week 24' int 1 <trtid> 0 <stratification factors> &c1 &c2 stratification
factors>*<visit> 0 0 &c1 & / e;
  estimate 'active vs PBO at Week 24' trt 1;
  repeated <visit>/subject=<subject id> type=un;
run;
```

where trtid is assigned as 0 at baseline, 0 for placebo group at Week 24 and 1 for active group at Week 24. &c1 and &c2 are the proportion of patients evaluated in each stratification level among all the patients.

Subgroup analysis for the primary endpoint

```
proc mianalyze parms=mixparms covb(effectvar=rowcol)=mixcovb;  
  class <treatment arm> <beta blocker use> <exercise modality> <subgroup> ;  
  =<base pvo2 > <base weight> <treatment arm> <beta blocker use> <Exercise modality>  
  modeleffects Intercept <base pvo2 > <base weight> <treatment arm> <beta blocker use>  
  <Exercise Modality> <subgroup>*<treatment arm>;  
run;
```

SAS codes to evaluate normality assumption for the primary endpoint

The normality assumptions for the ANCOVA analysis will be assessed by residual illustration. The outpred option in the above code stores residuals which are used to test the assumption of normality. Examination of residuals can be done using the following codes.

```
proc univariate data=work normal;  
var ScaledResid; QQPLOT ScaledResid;  
ods output QQPlot=qqplot;  
run;
```

SAS codes to perform CMH test

```
proc freq data=work;  
  tables <Beta blocker use>*<CPET modality>*<treatment arm>*<response Y/N>/CMH  
  exactcmh;  
  exact riskdiff (column=2) relrisk (column=2) commor.  
Run;  
where response is coded as Y=1, N=0.
```

SAS codes to rank observation

```
proc rank data=work out=rwork nplus1;  
Var chg;  
Ranks rchg;  
Run;
```

SAS code for proportional hazard Cox regression model

```
Proc phreg data=work;  
  Class <treatment arm>(ref=first) ;  
  Model <time>*< censor (1)>= ;  
  Strata <beta blocker use> <CPET modality> ;  
Run;
```

SAS code for stratified logistics regression model

```
Proc phreg data=work;  
  Class <treatment arm>;  
  Model <Response> (event='Y')= <treatment arm> <baseline covariates>/selection=stepwise  
  details;  
  Strata <beta blocker use> ;  
Run;
```

SAS code for EQ-5D-5L Index Value

```
*****  
*SAS syntax code for the computation of index*  
*values with the US TTO value set*  
*****  
  
data WORK.CAT;  
set WORK.CAT;  
  
if mobility eq 1 then disut_mo=0;  
else if mobility eq 2 then disut_mo=0.096;  
else if mobility eq 3 then disut_mo=0.122;  
else if mobility eq 4 then disut_mo=0.237;  
else if mobility eq 5 then disut_mo=0.322;  
  
if selfcare eq 1 then disut_sc=0;  
else if selfcare eq 2 then disut_sc=0.089;  
else if selfcare eq 3 then disut_sc=0.107;  
else if selfcare eq 4 then disut_sc=0.220;  
else if selfcare eq 5 then disut_sc=0.261;  
  
if activity eq 1 then disut_ua=0;  
else if activity eq 2 then disut_ua=0.068;  
else if activity eq 3 then disut_ua=0.101;  
else if activity eq 4 then disut_ua=0.255;  
else if activity eq 5 then disut_ua=0.255;  
  
if pain eq 1 then disut_pd=0;  
else if pain eq 2 then disut_pd=0.060;  
else if pain eq 3 then disut_pd=0.098;  
else if pain eq 4 then disut_pd=0.318;  
else if pain eq 5 then disut_pd=0.414;  
  
if anxiety eq 1 then disut_ad=0;  
else if anxiety eq 2 then disut_ad=0.057;  
else if anxiety eq 3 then disut_ad=0.123;  
else if anxiety eq 4 then disut_ad=0.299;  
else if anxiety eq 5 then disut_ad=0.321;  
  
disut_total=disut_mo+disut_sc+disut_ua+disut_pd+disut_ad;  
EQindex=1-disut_total;  
run;
```

Signature Manifest

Document Number: PRD-0381

Revision: 00

Title: CY 6031 - SAP Version 2 - A Phase 3, Multi-Center, Randomized, Double-blind, Placebo-controlled Trial to Evaluate the Efficacy and Safety of CK-3773274 in Adults with Symptomatic Hypertrophic Cardiomyopathy and Left Ventricular Outflow Tract Obstruction

Effective Date: 09 Oct 2023

All dates and times are in Pacific Time.

CY 6031 - SAP Version 2 - A Phase 3, Multi-Center, Randomized, Double-blind, Placebo- controlled Trial to Evaluate the Efficacy and Safety of CK-3773274 in Adults with Symptomatic Hypertrophic Cardiomyopathy and Left Ventricular Outflow Tract Obstruction

1: Electronic Approvals

Name/Signature	Title	Date	Meaning/Reason
[REDACTED]	Senior Director, Biostatistics	05 Oct 2023, 11:52:16 AM	Approved
[REDACTED]	SVP, Chief Medical Officer	05 Oct 2023, 11:54:20 AM	Approved
[REDACTED]	Vice President, Biometrics	05 Oct 2023, 06:10:52 PM	Approved
[REDACTED]	SVP, Regulatory Affairs & Quality	05 Oct 2023, 07:36:03 PM	Approved
[REDACTED]	VP, Clinical Research & Therapeutic Area Lead, Cardiovascular	09 Oct 2023, 01:39:31 PM	Approved
